8.4.2 Hematologic Toxicity

Reduced leukocyte or platelet counts are not anticipated ramucirumab-related AEs. ~~However, on the planned day of treatment, ramucirumab should only be administered if:~~

- ~~• ANC is $\geq 1000/\mu\text{L}$; and~~
- ~~• platelet count is $\geq 75,000/\mu\text{L}$.~~

9. CONCOMITANT THERAPY

9.1 Ramucirumab

Palliative and supportive care for other disease-related symptoms and for toxicity associated with treatment will be offered to all patients on this study. This may include but is not limited to antiemetic agents, opiate and nonopiate analgesic agents, appetite stimulants, and granulocyte and erythroid growth factors. Medical teams are advised to prescribe these agents according to American Society of Clinical Oncology (ASCO) or local guidelines.

The use of other chemotherapy, experimental medications, other anticancer therapy, immunotherapy, hormonal cancer therapy, radiation, surgery for cancer, or experimental medications is indicative that the patient's disease or clinical condition is worsening and should be discontinued from this study. Combining any other form of anticancer therapy with ramucirumab is strongly discouraged as there is no information supporting that this can be done safely in this clinical situation.

Ramucirumab has not been studied in conjunction with radiation. Therefore, it is recommended that sites contact the lead Lilly CRP or designate prior to administering palliative radiation. If palliative radiation is being administered to new symptomatic areas, this may represent progression of disease in which case the patient should discontinue ramucirumab therapy. Patients should not receive chronic antiplatelet therapy, including NSAIDs (including ibuprofen, naproxen, and others), dipyridamole or clopidogrel, or similar agents.

Aspirin is permitted at doses ≤ 325 mg once daily. Ongoing aspirin therapy at doses exceeding 325 mg/day is not permitted.

Anticoagulation therapy is permitted as follows:

At entry into the protocol, patients on full-dose anticoagulation must be on a stable dose (minimum duration 14 days) of oral anticoagulant or low molecular weight heparin. If on warfarin, the patient [Type here]

Pembrolizumab + Ramucirumab (Ver 2.5, Oct 2024)

must have an INR ≤ 3 and no active bleeding or pathological condition present that carries a high risk of bleeding (for example, tumor involving major vessels or known varices).

Patients who develop venous thromboembolism during protocol therapy may continue study therapy but must receive low molecular weight heparin, not oral anticoagulation.

The effects of ramucirumab on wound healing are not known. Bevacizumab (an antibody to VEGF-A ligand) is associated with a higher incidence of serious wound-healing complications.

In one study, 6 of 39 patients (15%) requiring surgery during or following bevacizumab experienced complications related to wound healing or bleeding; in a second study, complications were experienced by 1 of 25 patients (4%) requiring surgery (50). Hence, it is recommended that major surgery either be performed more than 28 days prior to enrollment or be postponed until at least 28 days after last dose of ramucirumab, when possible, and that subcutaneous venous access devices be placed at least 7 days prior to enrollment if their use is likely to be warranted. If major surgery is required during study therapy, the surgeon should be informed that the patient is receiving an agent that may be associated with a higher incidence of wound-healing complications. If subcutaneous venous access device placement is required during the course of protocol therapy, it is recommended that a 7-day treatment-free period occur both prior to and following placement.

Although emesis is not an expected adverse drug reaction to ramucirumab, the use of antiemetic agents is permitted at the discretion of the treating physician.

The use of analgesic agents is permitted at the discretion of the treating physician. Opiate and nonopiate analgesic agents are permitted (including acetaminophen); however, the use of NSAIDs and/or aspirin is prohibited as detailed above.

The use of appetite stimulants is permitted at the discretion of the treating physician.

Although neutropenia is not an expected adverse drug reaction of ramucirumab, the use of granulocyte colony stimulating factors (G-CSF) is permitted in accordance with ASCO or local guidelines.

The use of erythroid-stimulating factors (for example, erythropoietin) is permitted in accordance with ASCO or local guidelines.

The use of benzodiazepines, antidepressants, laxatives, and other agents that may be helpful in controlling disease-related symptoms are also permitted and encouraged, except as prohibited as outlined above.

[Type here]

[Type here]

[Type here]

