 - ✓ Total bilirubin $\leq 1.5 \times$ institutional upper limit of normal (ULN)
 - ✓ AST (SGOT)/ALT (SGPT) $\leq 3.0 \times$ institutional upper limit of normal unless liver metastases are present in which case it must be $\leq 5 \times$ ULN
 - ✓ Serum creatinine $\leq 1.5 \times$ institutional ULN
 - ✓ Glomerular filtration rate < 45 mL/min in assessed by standard methods in the laboratory
 - ✓ urinary protein is $\leq 1+$ on dipstick or routine urinalysis
 - ✓ (INR) ≤ 1.5 and (PTT) \leq x5 seconds above the ULN (unless receiving anticoagulation therapy). Patients on anticoagulation therapy with unresected primary tumors or local tumor recurrence following resection are not eligible.

[Type here]

[Type here]

[Type here]

11. Female patients of childbearing potential must have a negative pregnancy test (urine or serum), must not be breastfeeding and using adequate contraceptive measures.

Female patients must use a highly effective contraceptive measure from screening until 4 months after the last dose of drug. All methods of contraception (except for total abstinence) should be used in combination with the use of a condom by a male sexual partner for intercourse (see Restrictions below). (or vasectomy)

Female patients must have evidence of non-childbearing potential by fulfilling one of the following criteria at screening:

- a. Post-menopausal women defined as aged more than 50 years and amenorrhoeic for at least 12 months following cessation of all exogenous hormonal treatment.
- b. Documentation of irreversible surgical sterilisation by hysterectomy, bilateral oophorectomy, or bilateral salpingectomy, but not tubal ligation.

11-1. For the duration of the study and for 1 week after the last study drug administration, sexually active male patients must be willing to use barrier contraception i.e. condoms with all sexual partners. Where the sexual partner is a 'women of child-bearing potential' who is not using effective contraception, men must use a condom (with spermicide) during the study and for 6 months after the last dose of a study drug. (or vasectomy)

12. Biopsy during the screening window prior to dosing and at before cycle 3 (if clinically feasible)

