6.2 Exclusion Criteria

Patients who meet any of the following criteria will be excluded from participation in this study:

1. The patient has documented and/or symptomatic encephalitis, brain or leptomeningeal metastases.
2. The patient has experienced any Grade 3 to 4 GI bleeding within 3 months prior to enrollment.
3. The patient has experienced myocardial infarction, transient ischemic attack, cerebrovascular accident, or unstable angina, within 6 months prior to enrollment.
4. The patient has a history of deep vein thrombosis (DVT), pulmonary embolism (PE), or any other significant thromboembolism (venous port or catheter thrombosis or superficial venous thrombosis are not considered "significant") during the 3 months prior to first dose of protocol therapy.
5. Has received a live vaccine within 30 days prior to the first dose of study drug. Examples of live vaccines include, but are not limited to, the following: measles, mumps, rubella, varicella/zoster (chicken pox), yellow fever, rabies, Bacillus Calmette–Guérin (BCG), and typhoid vaccine. Seasonal influenza vaccines for injection are generally killed virus vaccines and are allowed; however, intranasal

[Type here]

[Type here]

[Type here]

Pembrolizumab + Ramucirumab (Ver 2.5, Oct 2024)

influenza vaccines (eg, FluMist®) are live attenuated vaccines and are not allowed

6. The patient has an ongoing or active infection, symptomatic congestive heart failure, unstable angina pectoris, symptomatic or poorly controlled cardiac arrhythmia, uncontrolled thrombotic or hemorrhagic disorder, or any other serious uncontrolled medical disorders in the opinion of the treating physician.
7. The patient has ongoing or active psychiatric illness or social situation that would limit compliance with treatment.
8. The patient has uncontrolled or poorly controlled hypertension (>160 mmHg systolic or >100 mmHg diastolic for >4 weeks) despite standard medical management.
9. The patient has a serious or nonhealing wound, ulcer, or bone fracture within 28 days prior to enrollment.
10. The patient has received chemotherapy, radiotherapy, immunotherapy, or targeted therapy for gastric cancer within 2 weeks prior to enrollment.
11. The patient has received any investigational therapy within 30 days prior to enrollment.
12. The patient has undergone major surgery within 28 days prior to enrollment, or subcutaneous venous access device placement within 7 days prior to enrollment.

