8.4 Special Treatment Considerations

8.4.1 Dose Adjustments and Delays

Ramucirumab

Dose modifications are permitted for ramucirumab in the setting of non-life-threatening, reversible Grade 3 and 4 AEs (that is, fatigue, anorexia, or fever) that resolve to Grade ≤ 1 within 1 treatment cycle (approximately 2 weeks). In this setting, ramucirumab may be readministered. If a second
[Type here] [Type here] [Type here]

Pembrolizumab + Ramucirumab (Ver 2.5, Oct 2024)

instance of such an event occurs, ramucirumab should be subsequently readministered at a dose of 6 mg/kg every other week. A second dose reduction to 5 mg/kg every other week is permitted for this level of event (Grade 3 and 4). If a Grade 4 AE occurs and is deemed at least possibly related to ramucirumab, then ramucirumab should be discontinued except in specific case of Grade 4 fever or Grade 4 laboratory abnormalities. If Grade 4 fever or laboratory abnormalities resolve to Grade ≤ 1 or pretreatment baseline within one treatment cycle (approximately 2 weeks), treatment with ramucirumab may be continued at the discretion of the treating physician. Criteria for dose reduction in the setting of hypertension or proteinuria and other AESIs are detailed in Section 11

Patients who enter the study with symptoms or laboratory values equivalent to NCI-CTCAE Version 4.03 Grade 1 to 2 AEs should not have dose reductions related to the persistence or mild worsening of those symptoms or laboratory values; dose reductions may be warranted if worsening of symptoms or laboratory values is clinically significant in the opinion of the patient's physician. Asymptomatic Grade 3 to 4 laboratory abnormalities should not result in dose interruptions, modifications, or discontinuation of protocol therapy unless determined to be clinically significant by the patient's physician (or unless otherwise specified in this protocol).

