11.1.2 Thrombotic Events

Physicians should perform all testing required to fully characterize arterial or venous thrombotic/vascular events. In the REGARD study, venous thrombotic events (VTEs) were more frequent on the placebo arm than on ramucirumab (all grade 7.0% versus 3.8%; and Grade 3 or greater 4.3% and 1.3%, respectively). Arterial thrombotic events (ATEs) occurred in patients treated with ramucirumab (1.7% all grade; 1.3% Grade 3 or greater) and in no patients treated with placebo. In RAINBOW, the overall incidence of all grade and Grade ≥ 3 VTEs and arterial thromboembolic events were low and similar in both treatment arms (ramucirumab plus paclitaxel vs. placebo plus paclitaxel: all grade VTEs [4.0% vs. 5.5%] and Grade 3 or greater VTEs [2.4% vs. 3.3%]; all grade ATEs [1.8% vs. 1.5%] and Grade 3 or greater ATEs [0.9% vs. 0.9%]).

Because therapy with antiangiogenic agents has been shown to be feasible in the setting of anticoagulation in patients with upper GI malignancies (12), patients who develop Grade 3 and 4 venous thrombotic events (deep vein thrombosis [DVT] or pulmonary embolism [PE]) may continue ramucirumab therapy if the event is not considered to be life-threatening in the opinion of the patient's physician, the patient is asymptomatic, and/or the event can be adequately treated with low molecular weight heparin-based therapy.

Patients with unresected primary tumors (or local recurrence) who develop Grade 3 and 4 venous thromboembolism may also receive anticoagulation and continue ramucirumab therapy (as detailed above), provided that the tumor does not confer an excessive bleeding risk, in the opinion of the patient's physician.

Grade 3 and 4 arterial thromboembolic events, or any PE/DVT occurring or worsening during anticoagulant therapy, require permanent discontinuation of ramucirumab therapy. Any venous

[Type here]

[Type here]

[Type here]

Pembrolizumab + Ramucirumab (Ver 2.5, Oct 2024)

or arterial event leading to discontinuation of ramucirumab therapy will be considered serious and should be reported via the SAE mechanism.

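### Section 9.1 lets patients with an on-study venous clot continue on heparin without exception, while Section 11.1.2 and Appendix 2 stop ramucirumab for good if the clot arises on anticoagulation

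*Combined protocol and SAP*

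**What the plan says.** Section 9.1 is the ramucirumab part of Concomitant Therapy. Its paragraphs on permitted anticoagulation cover two situations.

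- **At entry:** "At entry into the protocol, patients on full-dose anticoagulation must be on a stable dose", for at least 14 days, of an oral anticoagulant or LMWH.
- **On study:** "Patients who develop venous thromboembolism during protocol therapy may continue study therapy but must receive low molecular weight heparin, not oral anticoagulation". The choice of anticoagulant is the only condition.

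Section 11.1.2 is the toxicity rule for thrombotic events. It lets patients with Grade 3 or 4 venous events continue ramucirumab if the event is judged not life-threatening, the patient is asymptomatic, "and/or the event can be adequately treated with low molecular weight heparin-based therapy". It then sets a mandatory stop: "any PE/DVT occurring or worsening during anticoagulant therapy, require permanent discontinuation of ramucirumab therapy". Appendix 2 repeats that stop in the same terms among its discontinuation rules.

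**The concern.** The stop applies whatever the grade of the PE or DVT; what triggers it is that the patient is already anticoagulated. Section 9.1 does not separate those patients from patients having a first clot off anticoagulants, yet it expressly allows them into the trial. It is also a natural place to look when a clot has to be treated. A physician who relies on it alone could keep giving ramucirumab where Section 11.1.2 and Appendix 2 require it to end.

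There is a secondary effect on reporting. Section 11.1.2 treats any venous event that leads to stopping ramucirumab as serious and reportable. If ramucirumab continues under Section 9.1, that trigger does not fire, although other seriousness criteria in Section 10.2.3, such as hospitalization, may still apply.

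**Working it through.** **Side by side.** The plan gives no figure to reproduce, so the first check is textual.

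| Situation | Section 9.1 | Section 11.1.2 / Appendix 2 | Result |
|---|---|---|---|
| First venous clot, Grade 1-2, not anticoagulated | May continue, on LMWH | No stop | Agree |
| First venous clot, Grade 3-4, not anticoagulated | May continue, on LMWH | Section 11.1.2: may continue on conditions joined by and/or, one being treatability with LMWH | Largely agree |
| Anticoagulated at entry, then develops PE/DVT | May continue, on LMWH | Permanent stop of ramucirumab | Conflict |
| On LMWH for a first clot, then a new PE/DVT | May continue, on its wording | Permanent stop of ramucirumab | Conflict by extension |
| On LMWH, existing clot worsens | Not addressed | Permanent stop of ramucirumab | Section 9.1 silent |

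**Does another section settle it?**

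- Section 8.4.1 has its own stop: "If a Grade 4 AE occurs and is deemed at least possibly related to ramucirumab, then ramucirumab should be discontinued", with exceptions for fever and laboratory abnormalities. It does not reach lower-grade clots on anticoagulants.
- Section 8.4.1 also refers to Section 11, but for dose-reduction criteria.
- Section 6.3, to which Section 7.1 sends the reader for stopping treatment, has general clauses such as unacceptable toxicity. It neither lists nor points to the Section 11 stop rules.

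**Can the case occur?** Two eligibility rules narrow it without closing it. Section 6.1, item 9: "Patients on anticoagulation therapy with unresected primary tumors or local tumor recurrence following resection are not eligible". Section 6.2, item 4 excludes significant thromboembolism "during the 3 months prior to first dose of protocol therapy". A patient with a resected primary, no local recurrence and an older clot, or another reason for anticoagulation, can still enter.

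**How many, by the entry route?** Inputs:

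- n = 25 evaluable patients (Section 12).
- v = all-grade venous event rate on ramucirumab, from Section 11.1.2: 3.8% in REGARD, and 4.0% in RAINBOW, where ramucirumab was given with paclitaxel ("all grade VTEs [4.0% vs. 5.5" percent, ramucirumab arm first).
- a = share anticoagulated at entry. The documents do not give it; 5% to 15% is assumed, with v taken as the same in these patients as in the others.

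Expected number = n × v × a.

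- Low: 25 × 0.038 × 0.05 = 0.0475, about 0.05.
- High: 25 × 0.040 × 0.15 = 0.15.

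The chance of at least one such patient is 1 − (1 − v × a)^25:

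- Low: 1 − (1 − 0.0019)^25 = 0.05.
- High: 1 − (1 − 0.006)^25 = 0.14.

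At a = 0 the expected number is 0. If every venous event fell in an anticoagulated patient it would be 25 × 0.040 = 1.0, still at the 4.0% rate. Section 7.1 gives a maximum of 35 patients; at n = 35 the range is 35 × 0.0019 = 0.07 to 35 × 0.006 = 0.21.

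**The case against.** The strongest reply is that this is a general sentence beside a specific one. Section 9.1 deals with which anticoagulant to use and says only that patients may continue. Section 11 governs toxicity, and Section 11.1.2 gives both the permission and its mandatory exception. Section 10.2.5 lists venous thrombotic events among the events of special interest, so the reference in Section 8.4.1 does lead a careful physician to Section 11. Section 8.4.1 also lets the physician stop ramucirumab for toxicity at any time. All of this stands, and it is why the point is minor. It does not make Section 9.1 correct for the anticoagulated patient, because the rule there is stated without exception and the Section 8.4.1 reference does not mention stopping.

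Three stronger readings are tempting, and the documents do not support them.

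- **That the sections conflict for Grade 3-4 venous clots in general.** The and/or wording in Section 11.1.2 lets treatability with LMWH support continuing, which largely matches Section 9.1.
- **That Section 9.1 permits continuing when a clot worsens on LMWH.** It speaks of patients who develop a clot and of how to treat it. It says nothing about worsening.
- **That the number affected is two or more times larger.** Suppose 5% to 20% of first clots in the other patients recur or worsen on LMWH, a share r that the documents also do not give. Then 25 × v × [a + (1 − a) × r] runs from 25 × 0.038 × 0.0975 = 0.09 to 25 × 0.040 × 0.32 = 0.32. That sum includes worsening, which Section 9.1 does not address.

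**Conclusion.** The inconsistency holds, narrowly. It is clear for a patient anticoagulated at entry who then develops a PE or DVT. By extension it covers a new PE or DVT in a patient put on LMWH for a first clot.

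The size is well under one patient of 25: about 0.05 to 0.15 by the entry route, which rests on the assumed 5% to 15% and on venous event rates carried over from other ramucirumab trials. Those rates count all venous events, whereas the stop names PE and DVT, so the range leans high. The two eligibility limits also push the entry share down.

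The range counts patients who would meet the conflicting instructions. A reader might take it as the number wrongly kept on ramucirumab; that would need the further, unknown share of physicians who act on Section 9.1 alone. Nor do the sections force a breach, since stopping ramucirumab complies with both.

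This is a low-severity inconsistency about a safety stop. The response-rate analysis and the Simon two-stage design are unaffected.

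**What to change.** Amend the Section 9.1 sentence in two places. After the permission to continue, insert *subject to Section 11.1.2*. At the end, add a clause saying that ramucirumab must be permanently discontinued if a PE or DVT arises or worsens while the patient is on an anticoagulant. The permission for Grade 1-2 clots in patients not anticoagulated is kept, as is the LMWH requirement.

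No pointer in Section 6.3 is needed. If one is added, it should say discontinuation of ramucirumab only. Section 6.3 opens with patients being discontinued from the study, so a bare pointer could turn a ramucirumab stop into study withdrawal. The Synopsis continues pembrolizumab after intolerable ramucirumab toxicity.

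The cost is the wording change: no added procedures, visits or patients, and no change to the analysis. The rare affected patient loses ramucirumab, as Section 11.1.2 already requires. Whether pembrolizumab stops as well depends on a separate disagreement between the Synopsis and Section 7.1, which ends pembrolizumab when ramucirumab ends. This edit does not settle that.

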9.2 Pembrolizumab

Subjects are prohibited from receiving the following therapies during the Screening and Treatment Phase (including retreatment for post-complete response relapse) of this trial:

- Antineoplastic systemic chemotherapy or biological therapy
- Immunotherapy not specified in this protocol
- Chemotherapy not specified in this protocol
- Investigational agents other than pembrolizumab
- Radiation therapy
 - Note: Radiation therapy to a symptomatic solitary lesion or to the brain may be allowed at the investigator's discretion.

Live vaccines within 30 days prior to the first dose of trial treatment and while participating in the trial. Examples of live vaccines include, but are not limited to, the following: measles, mumps, rubella, varicella/zoster, yellow fever, rabies, BCG, and typhoid vaccine.

Systemic glucocorticoids for any purpose other than to modulate symptoms from an event of clinical interest of suspected immunologic etiology. The use of physiologic doses of corticosteroids may be approved after consultation with the Merk.

Subjects who, in the assessment by the investigator, require the use of any of the aforementioned treatments for clinical management should be removed from the trial. Subjects may receive other medications that the investigator deems to be medically necessary.

There are no prohibited therapies during the Post-Treatment Follow-up Phase.

10. EFFICACY AND SAFETY EVALUATION

10.1 EFFICACY

This study will assess the efficacy of ramucirumab when given in combination with pembrolizumab in patients with metastatic gastric or GEJ adenocarcinoma.

